**Table 14. Areas of Safety Interest Listing (Continued)**

ASI Grouping	Categories (ASI)	Search Criteria	Terms to Display	Include in AE Overview (Y/N)
Hepatic Events	Hepatic Events	Broad Hepatic failure, fibrosis and cirrhosis and other liver damage-related conditions (SMQ 20000013) Broad Hepatitis, non-infectious (SMQ 20000010) Broad Cholestasis and jaundice of hepatic origin (SMQ 20000009) Broad Liver related investigations, signs and symptoms (SMQ 20000008) Narrow Liver-related coagulation and bleeding disturbances (SMQ 20000015)	PTs	N

#### 8. Adjudicated events including CCVT

Table A4 (See Appendix) illustrates the events and sub-events that will be adjudicated along with which events will comprise the definition of a MACE event.

#### 9. Adverse Event per 100 Patient Years of Exposure in Study 1311.5 and Study M16-244

The treatment-emergent adverse events occurring during Study 1311.5 and Study M16-244 will be presented by event rate per 100 patient year. These will be

---

presented for any TEAEs, serious adverse events, AE of special interest in addition to MACE events.

AEs per 100 patient years of exposure is defined as the number of AEs divided by the total exposure in 100 patient years. Note that one event per preferred term per day per subject will be counted in the calculation of the number of AEs (i.e., a preferred term will not be counted twice on the same day for the same subject). See the calculation method below.

$$100 \times \frac{\text{Number of TEAEs}}{\text{Total Patient Years}}$$

where total patient years is defined as the sum of the study drug exposure (defined in Section 9.0) of all subjects normalized by 365.25, and rounded to one decimal place.

## 10. Safety Subgroup Analysis

The following subgroup analyses will be performed to evaluate the safety in the primary endpoint across demographic data, baseline disease characteristics for PsA.

Subgroup Factor	Categories
Age	< 55 years, ≥ 55 years
Sex	Male or Female
Race	White or Others
Prior TNFi use	Naïve or experienced
Concurrent MTX use	Yes or no

## 11. Listing of Adverse Events

The following additional summaries of AEs will be prepared.

- Listing of Subjects with TEAE of Area of Safety Interests
- Listing of Subjects with Pretreatment Serious Adverse Events
- Listing of Subjects with Treatment-Emergent Serious Adverse Events
- Listing of all adverse events that led to discontinuation of study drug

- Listing of all deaths

### **11.3 Analysis of Laboratory Data**

Changes from Baseline in Study 1311.5 in continuous laboratory parameters will be summarized by n, mean, standard deviation, minimum value, median, and maximum value for the group of subjects that received Placebo in Study 1311.5 and for the group of subjects that received Risankizumab in Study 1311.5.

Shift tables from Baseline to the final value (the last assessment during each treatment period) according to the normal range will be provided for each hematology, clinical chemistry parameter and urinalysis parameter. The laboratory data will be categorized as low, normal, or high based on the normal ranges of the laboratory used in this study. The shift tables will tabulate the number and percentage of subjects with Baseline in Study 1311.5 values below/within/above the normal range versus final values below/within/above the normal range.

Frequencies and percentages of subjects with post Baseline lab values meeting the following criteria in [Table 15](#) and [Table 16](#) will be summarized.

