The modified Total Sharp Score (mTSS) method, including distal interphalangeal joints, will be used to evaluate radiographic evidence of damage.¹ X-rays of hands, wrists and feet will be performed at two time points (Weeks 24 and 48, detailed in [Appendix C](#)). Images will be read centrally for each subject in a random order and without knowledge of time point, or subject identity, or treatment assignment in Study 1311.5. Subjects who prematurely discontinue from study drug will not be required to collect x-rays at each designated time point, unless they received a dose within the 16 weeks prior to the scheduled time point.

See [Appendix D](#) for instructions specific to Germany.

Clinical Laboratory Tests

Subject will be instructed in advance to attend study visits in a fasted state (8 hours no food and only water). If a patient comes in non-fasted where a fasting condition is required, the visit should be performed, the non-fasted condition documented on the laboratory requisition, and the patient reminded about the expected conditions.

Blood samples will be obtained for the laboratory tests listed in [Table 1](#) at the specified time points noted in [Appendix C](#) depending on the subject's status in the study. Blood draws should be performed after all clinical assessments and patient reported outcomes, ECGs, and vital sign determinations are obtained before study drug administration during a visit.

Urine samples will be obtained for urinalysis testing at the specified time points as listed in Table 1 and at the time points noted in [Appendix C](#). The central laboratory will be responsible for performing a macroscopic urinalysis (urine dipstick) on the collected urine specimens. Specified abnormal macroscopic urinalyses will be followed up with a microscopic analysis at the central laboratory.

A certified central laboratory will be utilized to process and provide results for the clinical laboratory tests. All abnormal laboratory tests that are considered clinically significant by the investigator will be followed to a satisfactory resolution. Laboratory abnormalities are considered to be adverse events only if they result in discontinuation from the study, necessitate therapeutic medical intervention, and/or if the Investigator considers them to be an adverse event.

Instructions regarding the collection, processing and shipping of these samples will be provided by the central laboratory chosen for this study.

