## 6.0 Analysis Conventions

### 6.1 Definition of Baseline

The last non-missing measure collected on or before the day of the first dose of study drug injection in Study 1311.5 for each randomized subject will be used as the Baseline for summary of demographics, disease characteristics and safety analyses. For efficacy endpoints except modified total Sharp score (mTSS), the baseline is defined as the last non missing pre-treatment observation prior to first dose in Study 1311.5. The Baselines for mTSS are defined as the last non-missing observation prior to Day 13 and closest to Day 1 in Study 1311.5.

For mTSS, data for Week 24 in Study 1311.5 and Week 24 in Study M16-244 are considered in analyses. In the context of visits corresponding to mTSS data collection

they will be referred to as Week 24 (Study 1311.5) and Week 24 (Study M16-244) respectively.

If multiple measurements are recorded on the same day, the worst of the multiple measurements will be used.

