## **6.4                   Definition of Analysis Windows**

All time points and corresponding time windows are defined based on Rx Days.

For efficacy analyses, laboratory parameters, and vital sign variables, analysis windows are constructed using the following algorithm:

- Determine the nominal Rx day for each visit (e.g., Week 4 [4 weeks after Baseline visit] equals Rx Day 29).
- In order to include all post baseline data, the first post-baseline interval starts on the first day after the first dose of study drug (Rx Day 2).

---

- Determine the window around a specific nominal Rx day by adding or subtracting half of the interval between adjacent visits (e.g., days between Week 2 and Week 4 is 14). The threshold between adjacent visits is determined by splitting the interval evenly between the visits. If the resulting split is between Rx days, then the threshold is determined as the midpoint between the adjacent visits. If the resulting split is on a Rx day, then the threshold is determined as being between that Rx day and the Rx day prior to it (e.g., the split between Week 2 and Week 4 would be between Rx Days 22 and 23).
- If more than one assessment is included in a time window the assessment closest to the nominal day will be used. If there are two observations equidistant to the nominal day, the one after the nominal day will be used in analyses. If more than one assessment is included on the same day, then the worst assessment on that day will be used in analyses. For laboratory values, if there are multiple measurements on the same day, average value will be used.

The protocol specified visits and corresponding time windows used in the various efficacy analyses, laboratory parameters, and vital sign variables, are presented in the following tables.

**Table 1. Analysis Windows for Efficacy Variables (PtGA, Patient's Assessment of PsA Pain Intensity, HAQ-DI, SF-36v2, TJC68, SJC66, PASI, BSA, sPGA, PhGA, hsCRP for DAS)**

Protocol Specified Visit Week	Lower Bound	Target Day	Upper Bound
0	1	1	1
4	2	29	57
12	58	85	127
24	128	169	211
36	212	253	295
48	296	337	351
52	352	365	378

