**Table 16. Criteria for Potentially Clinically Important Hematology Values**

Hematology Variables	Units	Definition of Potentially Clinically Important Current (Version 4) CTCAE Grade 3 or greater	
		Very Low	
Hemoglobin	g/dL		< 8.0
Platelets count	10  /L		< 50.0
WBC count	10  /L		< 2.0
Neutrophils	10  /L		< 1.0
Lymphocytes	10  /L		< 0.5

Though the protocol indicates utilizing the Rheumatology Common Toxicity Criteria (RCTC) scale for grading laboratory values, given that the National Cancer Institute Common Toxicity Criteria for Adverse Events (NCI CTCAE) scale includes a more comprehensive list of laboratory values; the lab analyses based on the NCI CTCAE scale will be presented.

For selected laboratory parameter with CTCAE a listing of all subjects with any laboratory determinations meeting CTC Version 4.0 (or later) of Grade  $\geq 3$  will be provided. For each of these subjects, the whole course of the parameter will be listed. For subjects with laboratory values with CTC  $\geq 3$  in addition to being a higher grade than the baseline CTC grade for that lab parameter, all of the laboratory parameters for those subjects will be listed.

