**Table 18. Criteria for Potentially Clinically Significant Vital Sign Findings**

Vital Signs Variables	Criterion	Definition of Potentially Clinically Important
Systolic Blood Pressure (mmHg)	Low	Value $\leq$ 90 mmHg and decrease $\geq$ 20 mmHg from Baseline
	High	Value $\geq$ 180 mmHg and increase $\geq$ 20 mmHg from Baseline
Diastolic Blood Pressure (mmHg)	Low	Value $\leq$ 50 mmHg and decrease $\geq$ 15 mmHg from Baseline
	High	Value $\geq$ 105 mmHg and increase $\geq$ 15 mmHg from Baseline
Heart Rate (bpm)	Low	Value $\leq$ 50 bpm and decrease $\geq$ 15 bpm from Baseline
	High	Value $\geq$ 120 bpm and increase $\geq$ 15 bpm from Baseline

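### SAP 11.3 counts out-of-limit laboratory values without requiring worsening from baseline and does not say which values feed the counts, so they can be biased in either direction

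*SAP*

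**What the plan says.** **The counts.** SAP 11.3 will summarize "Frequencies and percentages of subjects with post Baseline lab values meeting the following criteria", meaning the limits in Table 15 (13 chemistry parameters) and Table 16 (5 hematology parameters). Neither the sentence nor the tables refer to the subject's baseline value. Baseline for safety is "The last non-missing measure collected on or before the day of the first dose of study drug injection in Study 1311.5" (SAP 6.1).

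**Where the SAP does require worsening.** Table 18 pairs each absolute vital-sign limit with a change; the blood pressure criteria end in "mmHg from Baseline". In the text after Table 16, a listing of all laboratory parameters is restricted to subjects with a Grade 3 or higher value "in addition to being a higher grade than the baseline CTC grade for that lab parameter".

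**How laboratory values are selected.** SAP 6.4 names laboratory parameters as in scope and says "If more than one assessment is included in a time window the assessment closest to the nominal day will be used" and "For laboratory values, if there are multiple measurements on the same day, average value will be used". SAP 11.3.2 repeats the averaging rule. Table 6 gives post-dose windows from Day 2 to Day 378. In contrast, SAP 6.1 says of baseline "If multiple measurements are recorded on the same day, the worst of the multiple measurements will be used".

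**What the protocol generates.** Section 5.3.1.1 requires clinically relevant abnormal results to be confirmed and repeated until they settle, so several values in one window are foreseeable. It asks for fasted visits and, failing that, wants "the non-fasted condition documented on the laboratory requisition". The SAP does not mention fasting.

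**The concern.** Safety is the primary objective, and there is no concurrent control group against which pre-existing abnormalities would cancel. A reader will take the Table 15 and 16 frequencies as the laboratory safety result on risankizumab. As written, they can include subjects whose abnormality predates all study drug. Depending on a choice the SAP leaves open, they can also omit subjects who had a qualifying value. Two programmers following the same SAP could produce different counts.

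**Working it through.** There is no planned figure to reproduce: N is set by rollover (up to 180) and all analyses are descriptive. The check compares the rules and applies them to test cases with assumed laboratory values.

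**1. Worsening condition, side by side**

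| Output | Limit | Worsening from baseline |
|---|---|---|
| Table 15/16 counts (SAP 11.3) | yes | none |
| Table 18 vital signs | yes | change required |
| All-parameter listing (after Table 16) | Grade ≥ 3 | higher grade required |

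Omitting the condition can only raise a count of new abnormalities. The share of subjects beyond a limit at baseline who stay there is not in the documents. If it is assumed to be 0%, 1%, 2% or 5% of 180, then 0, 1.8, 3.6 or 9 subjects are counted without any change.

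**2. Same-day averaging, if applied**

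- ALT 6.0 and 3.6 × ULN: (6.0 + 3.6)/2 = 4.8. The limit is > 5.0, so the subject is not counted, although one value qualifies.
- Platelets 40 and 70: (40 + 70)/2 = 55. The limit is < 50, so again not counted.

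A mean never exceeds its maximum or falls below its minimum, so averaging can only lower the count.

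**3. Windows, if applied**

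Midpoints of the target days reproduce the Table 6 upper bounds: (29+85)/2 = 57, (85+169)/2 = 127, (169+253)/2 = 211, (253+337)/2 = 295, (337+365)/2 = 351, and 365 + 13 = 378.

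- *Unscheduled peak.* ALT beyond the limit on Day 60 lies in the Week 12 window (Days 58 to 127), 25 days from target. A Day 85 value is 0 days from target and replaces it.
- *Peak at a visit, then a repeat.* ALT 6.0 × ULN on Day 165 and 2.0 on Day 169: the Week 24 value is 2.0. Assume the visit falls uniformly within −4 to +4 days of target, with one normal repeat uniformly 1–7, 1–14 or 1–28 days later. The repeat displaces the peak in 19/63 = 30%, 20/126 = 16% or 20/252 = 8% of cases.
- *Early stop.* With a last dose on Day 85, the end-of-study visit 16 weeks later is Day 85 + 112 = 197, 28 days from the Week 24 target. An early end-of-treatment visit between about Days 142 and 196 is nearer and displaces it.
- *Late values.* 140 days after a Day 253 dose is Day 393, but windows stop at Day 378. The only planned contact after the Week 52 visit is a phone call, so this touches unscheduled or late samples only.

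**4. Net direction**

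Assume no pre-existing abnormality is missed.

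- 2% pre-existing, 2% of the rest new, 16% of new ones missed: truly new = 180 × 0.98 × 0.02 = 3.5; counted = 3.6 + 3.53 × 0.84 = 6.6.
- 0% pre-existing, 2% new, 30% missed: truly new = 3.6; counted = 3.6 × 0.70 = 2.5.

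The sign depends on rates that the documents do not give.

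**5. Scale**

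One subject is 1/180 = 0.56%. For 0 of 180, the exact two-sided 95% upper limit is 1 − 0.025^(1/180) = 2.0%. A few misclassified subjects therefore change the message.

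**The case against.** **The counts may already use every value.** The sentence in 11.3 is not by visit and reads naturally as any post-baseline value; on that reading the windows drop nothing. This stands, and makes the missed-value part conditional. But the SAP is explicit elsewhere: the Grade ≥ 3 listing covers any determination, and the vital-sign count in 11.4.2 specifies one value or more. Section 11.3 says neither, and 6.4 exempts nothing.

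**Other outputs keep the peaks.** A reader might infer that the counts do err both ways and that transient elevations disappear from the report. The documents do not support that. The Grade ≥ 3 listing shows the whole course for selected parameters. Section 11.3.2 lists subjects with ALT or AST of 3 × ULN or more and possible Hy's Law cases, and plans liver shifts to maximum and a plot of maxima. The subject averaging 4.8 × ULN would still be in the liver listing. What remains is that a listing does not correct a frequency table, and that the SAP does not say whether the maxima are taken over raw or averaged values.

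**Repeats follow an abnormal result.** The scheduled abnormal value is often the one nearest target. Correct: in the scenarios above it is kept in 70% to 92% of cases.

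**The tables do not claim treatment emergence.** They are labelled potentially clinically important, shift tables show baseline status, the limits are Grade 3, and exclusion criterion 14 removes some subjects with abnormal values. The pre-existing share may therefore be near zero. This argues for supplementing the plain count, not replacing it.

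**Same-day rules.** A reader might infer from 6.1 (worst) against 6.4 (average) that change from baseline is tilted towards improvement. The laboratory-specific averaging rule may govern baseline too, and the current counts use no baseline value. It is an ambiguity to settle, not an established bias.

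**Fasting.** It concerns glucose and triglycerides, 2 of 18 parameters, and nothing says the requisition note reaches the analysis database.

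**Conclusion.** The concern holds in a limited form. It is plain on the text that the Table 15 and 16 counts carry no worsening condition and so include abnormalities that predate study drug. It is conditional, on 6.4 and 11.3.2 governing these counts, that a qualifying value can be averaged or windowed out. The counts can therefore be biased in either direction; the documents do not show that they are, nor in which direction.

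The size rests on assumptions: 0 to 9 of 180 subjects counted without change if 0% to 5% were persistently beyond a limit, and 8% to 30% of scheduled-visit peaks displaced by a normal repeat if windows apply. The effect is confined to the frequency tables and possibly the liver maxima. It is worth correcting because it is cheap and bears on the primary objective.

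**What to change.** In SAP 11.3 and 11.3.2:

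- State that the Table 15/16 counts and the liver maxima (shift to maximum and the bilirubin–ALT plot) use every determination, scheduled or unscheduled, after the first M16-244 dose and up to 140 days after the last dose, taking the worst value with no windowing or same-day averaging. The start must be explicit: baseline belongs to Study 1311.5, so post-baseline read literally would bring in feeder-study values.
- Keep the plain count and add a row for subjects who meet the limit and have a higher CTC grade than at the Study 1311.5 baseline. The SAP already uses this condition in one listing. Name one CTCAE version for both grades, since Tables 15 and 16 cite different versions.
- Keep windows and averages for by-visit means.
- State one same-day rule for laboratory baseline, reconciling 6.1 with 6.4, before the worsening row is programmed.
- Optionally, flag non-fasted glucose and triglyceride values if fasting status is in the database.

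The cost is SAP wording, an extra row per criterion and a little programming. The required changes alter neither data collection nor trial conduct.

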**Table 15. Criteria for Potentially Clinically Important Chemistry Values**

Chemistry Variables	Units	Definition of Potentially Clinically Important Current (Version 3) NCI CTCAE Grade 3	
		Very Low	Very High
TBL	mcmol/L		> 3.0 × ULN
ALP	U/L		> 5.0 × ULN
SGOT/AST	U/L		> 5.0 × ULN
SGPT/ALT	U/L		> 5.0 × ULN
Albumin	g/L	< 20	
Glucose	mmol/L	< 2.2	> 13.9
Triglycerides	mmol/L		> 5.7
Creatinine	mcmol/L		> 3.0 × ULN
Potassium	mmol/L	< 3.0	> 6.0
Calcium	mmol/L	< 1.75	> 3.1
CK	U/L		> 5.0 × ULN
Total Cholesterol	mmol/L		> 10.34
GGT			> 5.0 × ULN

**Table 16. Criteria for Potentially Clinically Important Hematology Values**

Hematology Variables	Units	Definition of Potentially Clinically Important Current (Version 4) CTCAE Grade 3 or greater	
		Very Low	
Hemoglobin	g/dL		< 8.0
Platelets count	10  /L		< 50.0
WBC count	10  /L		< 2.0
Neutrophils	10  /L		< 1.0
Lymphocytes	10  /L		< 0.5

Though the protocol indicates utilizing the Rheumatology Common Toxicity Criteria (RCTC) scale for grading laboratory values, given that the National Cancer Institute Common Toxicity Criteria for Adverse Events (NCI CTCAE) scale includes a more comprehensive list of laboratory values; the lab analyses based on the NCI CTCAE scale will be presented.

For selected laboratory parameter with CTCAE a listing of all subjects with any laboratory determinations meeting CTC Version 4.0 (or later) of Grade  $\geq 3$  will be provided. For each of these subjects, the whole course of the parameter will be listed. For subjects with laboratory values with CTC  $\geq 3$  in addition to being a higher grade than the baseline CTC grade for that lab parameter, all of the laboratory parameters for those subjects will be listed.

### **11.3.1                   Variables and Criteria Defining Abnormality**

Clinical laboratory tests conducted in the study are listed in [Table 17](#).

**Table 17. Laboratory Tests**

Category	Test name
Haematology	Hematocrit (Hct) Hemoglobin (Hb) White Blood Cells/Leukocytes Platelet Count/Thrombocytes
Enzymes	AST (GOT) ALT (GPT) Alkaline Phosphatase (AP) Creatine Kinase (CK) Gamma-Glutamyl Transferase (GGT/γ-GT) Lactic Dehydrogenase (LDH) Amylase Lipase
Electrolytes	Calcium Sodium Potassium Chloride Bicarbonate
Substrates	Glucose BUN (blood urea nitrogen) Creatinine Bilirubin Total Albumin Cholesterol, total Triglycerides LDL-Cholesterol HDL-Cholesterol C Reactive Protein

**11.3.2 Statistical Methods****1. Analysis of Quantitative Laboratory Parameters (Hematology, Chemistry and Urinalysis)**

Changes from Baseline in Study 1311.5 to each scheduled visit and to the final value in continuous laboratory parameters will be summarized with mean, standard

deviation, median, minimum, Q1, Q3 and maximum. The Baseline and visit/final value means will also be presented for subjects who have both the Baseline and visit/final values (see Section 6.0 for the definition of Baseline and final values).

If there are multiple measurements on the same day, average value will be used.

Additional summaries will be presented for liver function tests including ALT or serum glutamic-pyruvic transaminase (SGPT), AST or serum glutamic-oxaloacetic transaminase (SGOT), alkaline phosphatase, and total bilirubin. Each laboratory value will be categorized as follows:

- $< 1.5 \times \text{ULN}$
- $\geq 1.5 \times \text{ULN} - < 3.0 \times \text{ULN}$
- $\geq 3.0 \times \text{ULN} - < 5.0 \times \text{ULN}$
- $\geq 5.0 \times \text{ULN} - < 10.0 \times \text{ULN}$
- $\geq 10.0 \times \text{ULN} - < 20.0 \times \text{ULN}$
- $\geq 20.0 \times \text{ULN}$

where ULN is the upper normal limit.

Shift tables of Baseline in Study 1311.5 to the maximum (relative to the normal range, i.e., the largest multiple relative to the upper limit of normal) values, and from Baseline to final value will be presented using these five categories. A listing of potentially clinically significant liver function laboratory values will be provided. The listing will include all subjects who met any of the following four criteria:

- $\text{ALT} \geq 3 \times \text{ULN}$ , or
- $\text{AST} \geq 3 \times \text{ULN}$ , or
- Alkaline phosphatase  $\geq 1.5 \times \text{ULN}$ , or
- Total bilirubin  $\geq 2 \times \text{ULN}$ .

[figure not shown]
A listing of possible Hy's Law cases, defined as those who meet all of the following conditions will be provided.

- ALT of  $> 3 \times \text{ULN}$  or AST of  $> 3 \times \text{ULN}$ ,
- associated with an increase in bilirubin  $\geq 2 \times \text{ULN}$ ,

- Alkaline phosphatase  $< 2 \times \text{ULN}$

In addition, a graphical summary highlighting potential cases of Hy's Law within each treatment group will be presented. The maximum on-treatment values of total bilirubin and ALT will be plotted each on a scale as multiples of the upper limit of normal. The figure will show areas that meet the criteria of cholestasis (total bilirubin  $> 2 \times \text{ULN}$ ), Temple's corollary (ALT  $> 3 \times \text{ULN}$ ) and Hy's Law as the combination of these two factors.

